12.1 General Approach

The general analysis plan begins with data description, including basic summary statistics such as means, standard deviations, correlations, cross-tabulations, and checking for outliers and missingness patterns. Data will be evaluated for normality through goodness-of-fit tests and q-q plots. If systematic deviations from normality are detected, the corresponding variables will be appropriately transformed using logarithm or other Box-Cox transformations.

We will examine spaghetti plots for visualization of the individual trajectories over time for the longitudinal hypothesis. The analyses for the longitudinal data will consist of computation of summaries across time and at each time point. For any fitted models, we will evaluate uncertainty in the model parameter estimates and assess goodness of fit for each model using standard techniques such as residual analysis and regression diagnostics.

For testing hypotheses we will use standard methods such as the t-test; we will use the Wilcoxon and chi-square tests when appropriate. With small sample size, we will use exact methods to compute the significance level. For testing proportions, we will use the standard arcsin transformation of proportions to stabilize variance and improve the normal approximation.

For each analysis discussed, we will also consider models that control for socio-demographic descriptors for the individuals in the study when available.

Missing data:

We will enroll a replacement participant if withdrawal occurs. To account for missing data, we will use inverse weighted probability analyses and imputation-based methods, and conduct sensitivity analysis to assess the stability of conclusions across analyses.

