12.4 Analysis of Secondary Endpoints

The secondary outcomes are:

- 1) *Alcohol use* measured as PDA, DDD, PEth, GGT at baseline and monthly after DBS implantation.
- 2) *Overall functioning* and disability measured with the WHODAS 2.0 scale at baseline and monthly after DBS implantation.
- 3) *Target engagement* measured with FDG-PET scans at 3 time points: pre-DBS baseline, post-DBS-OFF, and post-DBS-ON at 6 months.

The secondary outcome *PDA* as a measure of *alcohol use* is a proportion, collected at baseline and during follow-up and assessment visits (1 baseline and 12 monthly post-DBS measurements).

The other measures of alcohol use (*DDD, PEth, GGT*) and the overall functioning score *WHODAS 2.0* are continuous variables collected at baseline and during follow-up and assessment visits (1 baseline and 12 monthly post-DBS measurements).

Alcohol use and overall functioning

H3: LP DBS reduces alcohol use and improves overall functioning in subjects with severe AUD compared to baseline. Specifically, LP DBS increases PDA, and decreases DDD, PEth, GGT and WHODAS 2.0 score compared to baseline.

Primary analysis of H3: We will compare the baseline and 6-month time point using a paired t-test for each of the measures (PDA, DDD, PEth, GGT and WHODAS 2.0).

For PDA, the unit of analysis is the proportion of days X_{ij} in a month that participant i is abstinent during month j . To do the paired t-test, we use the two paired proportions X_{i0} (0 refers to the baseline measure) and X_{i6} (6 refers to the 6-month measure). We can use a t-test on the difference $D_i = (X_{i6} - X_{i0})$. This should be a reasonable approximation because the averages X over roughly $n = 30$

days should be approximately Gaussian. The Gaussian approximation can be improved by using the variance stabilizing transformation

$$Y_{ij} = 2 \arcsin \sqrt{X_{ij}}$$

Thus, we will do a t-test using the differences $2[\arcsin \sqrt{X_{i6}} - \arcsin \sqrt{X_{i0}}]$. With $n = 3$ participants, we have little power unless the effect is large (e.g., if PDA moves from 0.05 to 0.50).

Secondary analysis of H3: To assess the course of PDA, DDD, PhEt, GGT, and WHODAS 2.0 over the duration of the study while taking into account the repeated measures (13 measures for each participant – one at baseline and 12 post-DBS), we will use a **mixed-effects model**:

$$Z_{ij} = \mu + \alpha_i + \tau_j + \epsilon_{ij}$$

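### Does the small-sample exact rule in 12.1 undercut the paired t-test for H3 at n = 3, and does the 30-day argument leave that test unsupported?

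*Protocol*

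**What the plan says.** Section 12.1 is the general approach, worded identically in protocol and SAP. It names the t-test as a standard method and adds "we will use the Wilcoxon and chi-square tests when appropriate". The next sentence is "With small sample size, we will use exact methods to compute the significance level". It also plans a check of distributional shape: "Data will be evaluated for normality through goodness-of-fit tests and q-q plots".

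Section 12.4 is specific to H3: "We will compare the baseline and 6-month time point using a paired t-test for each of the measures", the measures being PDA, DDD, PEth, GGT and WHODAS 2.0. For PDA it supports the t-test with a sentence that begins "This should be a reasonable approximation because the averages X over roughly" 30 days. It continues with "The Gaussian approximation can be improved by using the variance stabilizing transformation" and "Thus, we will do a t-test using the differences", followed by the arcsine formula. It then warns that with three participants "we have little power unless the effect is large (e.g., if PDA moves from 0.05 to 0.50"). A mixed-effects model on 39 measurements is the secondary analysis of H3.

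Neither section gives an alpha level or sidedness for H3. H3 is worded directionally.

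**The concern.** Three things look wrong on a first reading.

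- **Two rules.** The study is small throughout, so the exact sentence in 12.1 could be taken to cover H3 as well. If it meant a signed-rank, sign or sign-flip test, the baseline to 6-month comparison could not reach 0.05 whatever the data. The example in 12.4 of an effect large enough to detect would then be impossible. An analyst free to choose between the rules after seeing the data could choose the result.
- **Normality at the wrong level.** Averaging over days makes each person's PDA estimate smoother. A paired t-test on 2 degrees of freedom needs the three between-visit differences to be roughly normal across people. The argument does not address that. It is also offered for PDA only, and protocol section 3.3 sets the baseline window at 180 days, not 30.
- **Power without a spread.** The power remark gives an effect but no SD of the participant differences.

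At stake is how much weight a small H3 p-value from three people could carry into later efficacy work.

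**Working it through.** The plan states no power, alpha or p-value for H3, so there is no figure of its own to reproduce. Two-sided 0.05 is assumed below.

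**1. Floor of an exact paired test.** Three pairs have 2³ = 8 sign patterns. The smallest p is 2/8 = 0.25 two-sided and 1/8 = 0.125 one-sided. Neither reaches 0.05. The floor applies only to the three-pair comparison, not to the mixed model.

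**2. The same data under the 12.4 t-test.** Take baseline PDA 0.05 (9 of 180 days) in all three participants, and 6-month PDA of 12, 15 and 18 days of 30, that is 0.40, 0.50 and 0.60. These values are illustrative.
- Differences 2[arcsin√X₆ − arcsin√X₀]: 0.918, 1.120, 1.321. Mean 1.120, SD 0.201.
- t = 1.120 / (0.201/√3) = 9.63 on 2 df.
- With 2 df, two-sided p = 1 − t/√(t² + 2) = 0.011. The 95% CI is 0.62 to 1.62.
- Exact signed-rank p = 0.25.

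The two readings therefore give different results, and what matters is which one the text supports.

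**3. Which reading the text supports.** In 12.1 the exact sentence comes straight after the Wilcoxon and chi-square tests. Those are the tests for which software offers both a large-sample and an exact p-value. A t-test p-value is already exact when the differences are normal. Section 12.4 then names the t-test for each H3 measure and writes out its differences for PDA. A specific section following a general one governs.

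**4. Normality across people.** Averaging over days is sufficient only if all participants share one true change, or if the true changes are themselves normal. Two assumed departures show the exposure, by simulation with n = 3 and a nominal 95% paired-t interval:

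| Assumed shape of the differences | Shapiro-Wilk rejects at 5% | Interval misses true mean |
|---|---|---|
| Normal | 5.0% | 5.0% |
| Exponential | 7.2% | 11.5% |
| Half no change, half the full 1.12 shift, plus day noise | 6.9–8.5% | 13–18% |

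The criticism is right: the argument does not secure normality, and three values cannot test it.

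**5. The power remark.** The shift is 2[arcsin√0.50 − arcsin√0.05] = 1.120. Day-noise variance, with days assumed independent, is 2/30 = 0.0667 for a 30-day baseline and 1/30 + 1/180 = 0.0389 for a 180-day baseline. Noncentral-t power on 2 df, with total variance equal to the squared between-participant SD plus day noise:

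| Between-participant SD (assumed) | Power |
|---|---|
| 0 | 94–99% |
| 0.2 | 83–91% |
| 0.3 | 71–77% |
| 0.5 | 47–50% |
| 1.0 | 20% |

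For 80% power the standardised difference must be 3.264, so the total SD may be at most 1.120/3.264 = 0.343. The remark holds for modest spread and fails for wide spread. The documents give no spread, so it is not shown to be wrong.

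**6. What an edit would change.**
- Saying that the t-test governs H3 confirms the natural reading.
- Rewording the 30-day sentence leaves the same test and the same p-value.
- Individual trajectories, summaries at each time point and an assessment of uncertainty in fitted models are already planned in 12.1.
- A numerical power statement would need an SD that nobody has. Its limits would also be fragile. The formula puts the between-participant limit for a 30-day baseline at √(0.343² − 0.0667), about 0.23, but simulation with binomial day counts gives only about 77% power there.

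**The case for a change.** The strongest case for a change is that the exact sentence is not expressly limited to Wilcoxon and chi-square, and no trigger is given for moving to Wilcoxon. The choice moves p from 0.25 to about 0.01 on identical data. The secondary objective speaks of demonstrating preliminary efficacy, so such a p-value could be quoted later. The repair would cost a few sentences and keep the sponsor's test.

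Part of this stands. The 30-day rationale is incomplete, it does not extend to the other four measures, and the interval can under-cover when people respond very differently. A one-line clarification would do no harm.

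The claim of a real conflict does not stand. It requires reading exact methods as a rank or sign-flip test and then letting a general sentence override a written-out analysis. Nor does the plan treat normality as settled: it speaks of a reasonable approximation that can be improved, and it volunteers that power is low. The objective itself is labelled preliminary.

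**Conclusion.** No change to the plan is needed. The apparent clash between 12.1 and 12.4 is a gap that an analyst fills sensibly: the paired t-test governs the H3 baseline to 6-month comparisons, and exact levels apply to Wilcoxon and chi-square tests where those are used. Under the unlikely alternative reading the floor would be 0.25 two-sided or 0.125 one-sided.

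The normality argument is weaker than it sounds. Under the assumed departures the nominal 5% miss rate becomes roughly 11% to 18%. Correcting the sentence would alter no test and no result. H3 is secondary in a three-person safety and feasibility pilot, the primary endpoints do not depend on it, and no decision rule in the documents uses an H3 p-value. Readers should treat any H3 p-value as conditional on normality and look first at the three individual changes.

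This rests on an assumed alpha of 0.05, assumed independence of days, and assumed shapes and SDs for the participant differences. The documents supply none of these.

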11.2 Other Criteria Requiring Discontinuation

If participants turn their DBS system off more than 50% of the time, which is unprompted by adverse effects, and if they continue to turn it off after discussion with the team, they will be withdrawn from the study and their DBS explanted.

Beginning chemotherapy or other investigational medications after enrollment will result in the subject's discontinuation from the study.

Beginning anticoagulation after enrollment and before DBS implantation will result in the subject's discontinuation from the study.

If a patient no longer wishes to continue their participation in the study, they may elect to withdrawal from the study. Normal recruitment procedures will resume to replace any participant withdrawals (see recruitment description in section 5.4).

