12.2 Sample Size Determination

Since this study is primarily designed for the assessment of safety and feasibility, a cohort of 3 patients was decided upon per clinical judgement and experience.

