with random effect α_i for subject, a fixed time effect τ_j , and the error term (unexplained variation) ϵ_{ij} . We will have 39 measures (3 subjects times 13 measures per subject at months 0 to 12). For PDA, we will use the arcsin-transformed proportions described above to improve Gaussian approximation by stabilizing the variance.

Target engagement

H4: LP DBS will result in circuit specific target engagement measured with FDG-PET.

H4a. CGM (cerebral glucose metabolism) as measured with $[^{18}\text{F}]$ FDG-PET in pre-defined cortico-limbic ROIs will be increased in post-DBS-ON compared to pre-DBS and to post-DBS-OFF conditions.

H4b. DBS-induced increases in CGM (%) at the 6-month time point will be associated with decreased alcohol use (PDA, DDD).

Analysis of H4(a): For each ROI in each of the scan types we will run a one-way Repeated Measures (RM) ANOVA comparing CGM between the 3 time points (baseline pre-DBS, DBS-OFF, and DBS-ON at 6 months), with post-hoc comparisons of DBS-ON vs. post-DBS-OFF, and DBS-ON vs. baseline.

Analysis of H4(b): We will use Pearson's correlation to assess the relationship between changes in CGM between post-DBS-OFF and 6 months and corresponding changes in measures of alcohol (PDA, DDD).

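### With three participants, participant-level weighting cannot show what a missing month-6 result would do to the alcohol-use findings, and cross-participant imputation has only two donors

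*Protocol*

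**What the plan says.** Section 12.1 (General Approach, Missing data) is worded the same in the Protocol and the SAP. It first says "We will enroll a replacement participant if withdrawal occurs", and Protocol 11.2 repeats this: "Normal recruitment procedures will resume to replace any participant withdrawals". It then says "we will use inverse weighted probability analyses and imputation-based methods, and conduct sensitivity analysis to assess the stability of conclusions". It gives no response model, imputation model, predictors or missing-data assumption, and does not say whether a replaced participant's data remain in the analysis.

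Section 12.2 sets the sample: "a cohort of 3 patients was decided upon per clinical judgement and experience". Section 12.4 gives the main analysis of H3 (alcohol use and functioning): "We will compare the baseline and 6-month time point using a paired t-test for each of the measures". The secondary analysis is a mixed model "while taking into account the repeated measures (13 measures for each participant"; the section counts 39 rows in all. Section 12.4 also concedes that with three participants "we have little power unless the effect is large (e.g., if PDA moves from 0.05 to 0.50").

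**The concern.** The plan presents weighting and imputation as the check on whether conclusions are stable when data are missing. Both learn about the missing result from people who were observed. In the paired month-6 comparison, one missing value leaves two such people. A check that cannot depart from what those two showed may look like reassurance while saying nothing about the third.

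What is at stake is the reading of the preliminary efficacy results. If both completers improved and the third participant's result is unknown, the reported stability analysis could agree closely with the complete-case result simply because it had no means of disagreeing.

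**Working it through.** **Inputs.** Three participants (12.2); one baseline-to-month-6 difference each (12.4); 13 measures per participant (12.4); example PDA change from 0.05 to 0.50 (12.4). Assumed here: one month-6 value is missing, weights are normalised to sum to one, and tests are two-sided at 5% (the plan states no alpha).

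**The plan's own count.** 3 × 13 = 39 rows, which reproduces.

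**Weighting at participant level, one of three missing.**
- *No covariate.* The response probability is 2/3, so each completer has weight 1/(2/3) = 1.5. Normalised, this is 0.5/0.5, which is complete-case analysis exactly.
- *One continuous covariate, missing person lowest or highest.* This is 2/3 of orderings (0.672 of 4,000 simulated draws). The logistic model separates and has no finite maximum-likelihood fit. Fitted probabilities for the completers tend to 1 and normalised weights to 0.5/0.5.
- *One continuous covariate, missing person in the middle.* This is the other 1/3 of orderings. The model can be fitted. Covariate values 40/45/60 give weights 0.614/0.386, and 40/41/70 give 0.666/0.334. In simulation the larger share had median 0.61 and maximum 0.67.
- *One binary covariate, missing person sharing a level with one completer.* Weights are 2 and 1, or 0.667/0.333. With illustrative results of 0.3 and 0.9 the weighted mean is (2 × 0.3 + 0.9)/3 = 0.50, against 0.60 for complete cases.

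In every case the estimate is w·d₁ + (1 − w)·d₂ with 0 ≤ w ≤ 1, so it lies between the two completers' changes.

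**Size, using the plan's example for both completers.** Each changes by 0.50 − 0.05 = 0.45.

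| Third participant at month 6 | Mean change in PDA |
|---|---|
| Any normalised weighting | 0.45 |
| Stays at baseline (change 0) | (0.45 + 0.45 + 0)/3 = 0.30 |
| All days drinking (change −0.05) | (0.45 + 0.45 − 0.05)/3 = 0.28 |
| All days abstinent (change 0.95) | (0.45 + 0.45 + 0.95)/3 = 0.62 |

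The two extremes are 1/3 apart, and weighting shows none of that range.

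**Cross-participant imputation of month 6.** There are two donors and 1 degree of freedom for between-person variance. The 95% range of a drawn standard deviation is about 0.45 to 32 times the observed one, from √(1/5.024) and √(1/0.000982). The imputed values are driven mainly by that uncertainty.

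**Longitudinal data.** One participant lost after month 6 leaves 39 − 6 = 33 rows; lost after month 1, 39 − 11 = 28 rows. A participant's own earlier or later visits can therefore inform a gap, and a pooled visit-level response model has more than three rows. Section 12.1 specifies neither.

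**The case against.** The strongest reply has four parts.

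1. *Weighting does not always collapse.* This stands. A reader might infer that with any covariate the weights either equal complete-case weights or do not exist. The middle-ranked and shared-level cases above refute that. What remains is that such weights rest on a model fitted to three points and still only mix two people.

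2. *Imputation need not draw on two people.* This stands for sporadic missed visits, where the participant's own months are available. Protocol 7.4 also allows weekly drinking assessment by telephone if 30-day recall is difficult. The two-donor limit applies to imputing month 6 across participants.

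3. *Withdrawals are replaced.* After replacement, three people may have month-6 data, so a drop to two pairs does not follow automatically. But the plan does not say whether the withdrawn participant still counts. Protocol 11.2 withdraws participants who persistently switch the device off, so departure need not be unrelated to the outcome. Replacement leaves the question open.

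4. *The consequence is small, and much of the remedy is already planned.* The safety and feasibility criteria in 12.3 rest on adverse events, recruitment, visit completion and DSMB judgement, and do not use these methods. The plan admits little power for H3, and already includes the mixed model, individual trajectory plots and checks of missingness patterns. All of this stands. It limits the importance of the point but does not make weighting a useful stability check.

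A reader might also infer that missing visits mean relapse, so that the results are biased towards benefit. The documents give no figure for this; it is a possibility to be bounded. Likewise, the fall in the paired test from 2 to 1 degrees of freedom (critical t 4.30 to 12.71) comes from losing a pair and not from choosing weighting.

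**Conclusion.** The point holds in a limited form. For the paired month-6 comparison with one value missing, participant-level weighting is usually complete-case analysis or has no finite fit. Otherwise it redistributes weight between two people, to about 0.67/0.33. It cannot reveal a third result outside their range. In the plan's own example it returns 0.45 whatever the weights, while the three-person mean could be anywhere from 0.28 to 0.62. Cross-participant imputation of that value has two donors.

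This rests on one missing month-6 value among three analysed participants and on normalised weights. The example is illustrative and on the untransformed PDA scale; the planned test uses the arcsine scale, where the same range argument applies to the transformed changes. The documents do not support a claim that the methods fail for every gap, or that the primary safety and feasibility conclusions are affected. The change is worth making because a more informative check is available at little cost.

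**What to change.** In section 12.1 of both documents, drop participant-level weighting and cross-participant imputation as the stability check, and state instead:

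- **Main handling.** The mixed model of 12.4, fitted by likelihood to all observed months. Say that it assumes data are missing at random, and is therefore not itself the check on that assumption.
- **PDA bounds.** Repeat the month-6 analysis with all missing days counted as drinking days, then with all counted as abstinent days, and report both. Baseline drinking is not a lower bound: Protocol 8.1 accepts that alcohol use may worsen with stimulation, and 11.1 provides for drinking above twice baseline.
- **DDD, PEth, GGT and WHODAS 2.0.** Show a version with the baseline value substituted beside the observed-data result, labelled as a sensitivity case and not a bound. Drinks per drinking day is undefined under full abstinence, and the documents give no abstinence value for GGT or WHODAS 2.0.
- **Withdrawals.** Keep the observed data of withdrawn participants in the analysis alongside any replacement.
- **Reporting.** List missing visits and their reasons by participant.

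The cost is a change of wording and a few extra summary lines; the model is already planned. The drawback is that the bounds can be wide: up to 1/3 on mean PDA change for one wholly missing month-6 value among three participants.

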12.2 Sample Size Determination

Since this study is primarily designed for the assessment of safety and feasibility, a cohort of 3 patients was decided upon per clinical judgement and experience.

12.3 Analysis of Primary Endpoints

The primary outcomes are:

- 1) *Safety and tolerability* measured as incidence of any serious adverse effect (AE), and incidence rate and severity of AEs that are definitely, probably, or possibly related to LP DBS throughout the study duration.
- 2) *Feasibility* measured as recruitment rate and completion rates of follow-up visits and assessments throughout the study duration.

The primary outcomes will be assessed continuously throughout the study.

H1. LP DBS for severe AUD will be deemed safe and well-tolerated by DSMB.

H1.a. LP DBS for severe AUD will not result in any serious adverse effects.

H1.b. The incidence rate of AE will be similar to standard of care DBS per the DSMB judgement.

H2. LP DBS for severe AUD will be deemed feasible.

H2.a. We will successfully recruit 3 participants for the study.

H2.b. Participants will complete >80% of all study follow-up visits and assessments.

Safety, tolerability, and feasibility will be assessed continuously throughout the study. We will screen for AEs using 4 approaches: 1) patient self-report, 2) clinical evaluations (medical, neurologic, and psychiatric), 3) questionnaires (e.g., screening for depression, suicidality, anxiety, apathy, mania) and 4) neuropsychological evaluation to screen for any LP DBS effects on various cognitive domains. Every AE will be evaluated for severity, expectedness and relatedness, and reported to the DSMB.

Safety and tolerability: The study will be deemed safe and tolerable if no serious AE that are definitely, probably, or possibly related to LP DBS occur during the study and if the AE severity and rate are not higher than standard of care DBS per DSMB's assessment.

Feasibility: the study will be deemed feasible if we successfully recruit the proposed number of participants and if participants complete >80% of all study follow-up visits and assessments.

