11.1 Adverse Events Requiring Discontinuation

Safety Monitoring Boundaries: Every adverse effect (AE) will be evaluated for severity, expectedness and relatedness and reported to the DSMB. The study will be discontinued (pending DSMB review) if any of the following occurs:

- A higher rate or severity of AE that are definitely, probably, or possibly related to LP DBS compared to standard of care DBS, as assessed by the DSMB.
- Any death, suicide attempt, disability, or other serious AE that is definitely, probably, or possibly related to LP DBS.
- Increased alcohol use in one participant compared to baseline ($>2x$ baseline DDD or $<2x$ PDA) that did not improve with adjusting DBS settings, as identified by AUD assessments in 3 consecutive follow-up visits.

If the study team proposes a well-justified and implementable plan on mitigation of such events, then the study could resume if the DSMB, IRB, and FDA agree.

All other serious adverse events and unexpected events will be reported to and discussed with the DSMB prior to continuing protocol enrollment. The occurrence of a serious adverse event will be grounds for unblinding the data for that participant.

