12.3 Analysis of Primary Endpoints

The primary outcomes are:

- 1) *Safety and tolerability* measured as incidence of any serious adverse effect (AE), and incidence rate and severity of AEs that are definitely, probably, or possibly related to LP DBS throughout the study duration.
- 2) *Feasibility* measured as recruitment rate and completion rates of follow-up visits and assessments throughout the study duration.

The primary outcomes will be assessed continuously throughout the study.

H1. LP DBS for severe AUD will be deemed safe and well-tolerated by DSMB.

H1.a. LP DBS for severe AUD will not result in any serious adverse effects.

H1.b. The incidence rate of AE will be similar to standard of care DBS per the DSMB judgement.

H2. LP DBS for severe AUD will be deemed feasible.

H2.a. We will successfully recruit 3 participants for the study.

H2.b. Participants will complete >80% of all study follow-up visits and assessments.

Safety, tolerability, and feasibility will be assessed continuously throughout the study. We will screen for AEs using 4 approaches: 1) patient self-report, 2) clinical evaluations (medical, neurologic, and psychiatric), 3) questionnaires (e.g., screening for depression, suicidality, anxiety, apathy, mania) and 4) neuropsychological evaluation to screen for any LP DBS effects on various cognitive domains. Every AE will be evaluated for severity, expectedness and relatedness, and reported to the DSMB.

Safety and tolerability: The study will be deemed safe and tolerable if no serious AE that are definitely, probably, or possibly related to LP DBS occur during the study and if the AE severity and rate are not higher than standard of care DBS per DSMB's assessment.

Feasibility: the study will be deemed feasible if we successfully recruit the proposed number of participants and if participants complete >80% of all study follow-up visits and assessments.

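### Protocol and SAP 12.3: the relatedness limit falls on related AEs in the safety outcome but on serious AEs in the verdict rule, so the verdict's AE comparison is unrestricted while 3.3, 11.1 and 11.3 restrict it

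*Protocol*

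**What the plan says.** Section 12.3 is the same in the protocol and the SAP, so neither resolves the other. It contains four statements on safety.

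- Outcome 1 is "incidence of any serious adverse effect (AE), and incidence rate and severity of AEs that are definitely, probably, or possibly related to LP DBS".
- H1.a: "LP DBS for severe AUD will not result in any serious adverse effects".
- H1.b: "H1.b. The incidence rate of AE will be similar to standard of care DBS per the DSMB judgement".
- The verdict rule requires "no serious AE that are definitely, probably, or possibly related to LP DBS occur during the study and if the AE severity and rate" to be no higher than with standard of care DBS, in the DSMB's assessment.

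Elsewhere in the protocol:

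- Section 10 defines an adverse effect irrespective of causal relationship. A serious one includes death and inpatient hospitalization, with no causal limit.
- Section 3.3 bases safety and tolerability on adverse events associated with DBS implantation and stimulation, to be compared with DBS side effects in approved indications. Section 10 defines association as a reasonable possibility of causation.
- Section 11.1, repeated in 11.3, makes this a trigger for discontinuation pending DSMB review: "A higher rate or severity of AE that are definitely, probably, or possibly related to LP DBS compared to standard of care DBS". The serious-AE trigger there is likewise limited to related events.

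**The concern.** Safety is the primary objective, and with three participants a single event can carry the result, so the events that count must be fixed beforehand. In 12.3 the relatedness limit changes place between what is measured and what is judged.

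The second part of the rule matters most. Participants have severe AUD and advanced liver disease, and can be expected to have adverse events from those conditions. The complications that section 8.1 reports for DBS are grouped as systemic, intracranial, neurologic, hardware and incisional. Counting disease-related AEs on the trial side pushes the comparison towards a finding of higher than standard care, for a reason unconnected with LP DBS.

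The first part is a smaller problem. A serious AE judged unrelated belongs to the primary outcome as written, but not to the serious-AE condition of the verdict.

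**Working it through.** There is no plan figure to reproduce: the sample size of 3 rests on clinical judgement (12.2), and no margin or error rate is attached to the safety verdict. The check is a comparison of event sets.

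**Scope of each statement, read literally**

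| Statement | Serious AEs | AE rate and severity |
|---|---|---|
| Outcome 1 (12.3) | any | related |
| H1.a (12.3) | those LP DBS results in | not addressed |
| H1.b (12.3) | not addressed | unrestricted (rate only) |
| Verdict rule (12.3) | related | unrestricted |
| Discontinuation and stopping (11.1, 11.3) | related | related |
| Endpoint definition (3.3) | associated with DBS | associated with DBS |

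The verdict rule is the reverse of outcome 1 in both columns. It agrees with 11.1 and 11.3 on serious AEs and disagrees on AE rate and severity.

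**Four kinds of event traced through the table**

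1. Serious and related: counts everywhere that serious AEs are addressed. No conflict.
2. Non-serious and related: counts in outcome 1, H1.b, the second part of the rule and 11.1. No conflict.
3. Serious and unrelated, such as an admission judged unrelated to LP DBS: counts in outcome 1. It does not count in the first part of the rule or in 11.1. It does enter the second part of the rule, because that part has no relatedness limit.
4. Non-serious and unrelated: does not count in outcome 1 or in 11.1, but does count in H1.b and the second part of the rule.

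Kinds 3 and 4 create the inconsistency. Enough of either could raise the unrestricted AE rate or severity above standard DBS while the 11.1 comparison stays within bounds.

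**Alternative parsing.** The closing relatedness clause of outcome 1 could be read as covering both of its items. That removes the conflict over serious AEs, but the second part of the rule and H1.b remain unrestricted.

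**Scale, for illustration only.** The documents give no rate of unrelated serious AEs. The nearest figure is the 45% ten-year mortality for compensated advanced disease (2.2).

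- Constant hazard: −ln(0.55)/10 = 0.0598 per year.
- Follow-up: surgery at about Day 20 (assumed) to Day 412 (Appendix A) = 392 days = 1.073 years.
- Per participant: 1 − exp(−0.0598 × 1.073) = 0.062.
- At least one death in three: 1 − (1 − 0.062)³ = 0.175, about 18%.
- Over 12 months instead: 1 − 0.55^(1/10) = 0.058, and 1 − (1 − 0.058)³ = 0.164.

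This is all-cause mortality. Exclusions for decompensated disease, coagulopathy and life expectancy under 18 months (5.3) make it likely to be too high.

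**The case against.** The strongest reply is that the plan has a single pass/fail statement, the verdict rule, and that outcome 1 only says what is measured. Measuring all serious AEs while judging on related ones is coherent. Sections 3.3, 11.1 and 11.3 show that the authors meant the comparison with standard DBS to cover related events, so the second part of the rule can be read that way in context. Every AE is graded for relatedness and reported to the DSMB, each serious AE suspends the study until classed as study-related or unrelated (13.5), and causality that is unknown and questionable is classified as associated for reporting (10.2).

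Much of this stands. Outcome 1 sets no threshold, so an unrelated serious AE does not by itself defeat the safety claim. The safeguards also limit any choice made after the event. However, grading supplies the data without saying which grades enter the verdict's AE rate. Study-related (13.5) is also not the same as related to LP DBS. The reading that rescues the rule has to be imported from other sections, and 12.3 itself states it differently.

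A reader might go further and infer that one unrelated death or admission fails H1.a yet passes the verdict. The documents do not support this. H1.a is worded causally and agrees with the first part of the rule; at most it is ambiguous because it names no relatedness grades. Nor is a pass assured, because the unrelated event enters the unrestricted second part.

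**Conclusion.** The primary safety event set is inconsistent as written in protocol 12.3 and SAP 12.3. The consequential defect is the unrestricted AE comparison in the second part of the rule and in H1.b, set against the restricted one in 3.3, 11.1 and 11.3. The different treatment of serious AEs in outcome 1 and the rule is secondary. This is a moderate problem of definition in a descriptive, DSMB-judged pilot and is worth correcting before events accrue.

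Its effect on the verdict cannot be quantified from the documents. A reader might assume that 20% to 50% of participants have an unrelated serious AE and take 1 − 0.8³ = 49% to 1 − 0.5³ = 88% as the share of trials in which the definitions disagree. That does not follow: the input rate is not in the documents, and the result is only the chance of at least one such event. Disagreement would also require no related serious AE, a pass on the second part of the rule, and a threshold that outcome 1 lacks. The mortality figure of about 18% carries the same caution. It rests on constant hazard, an assumed surgery day and all-cause deaths, and shows only that such events are not remote.

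The conclusion rests on reading 12.3 literally with the section 10 definitions, not on any of these rates.

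**What to change.** In protocol 12.3 and SAP 12.3:

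1. Reword the second part of the verdict rule and H1.b so that both refer to AEs graded at least possibly related to LP DBS, the set already used in 11.1.
2. State that H1.a and the serious-AE part of the verdict use that same related set.
3. Keep all-cause serious AE incidence visible: report it as n/3 with an exact confidence interval beside the verdict, stated to be descriptive and outside the pass/fail rule. Reword outcome 1 so that this role is clear.

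The cost is a few sentences in two documents and one extra table row. No new data are needed, since seriousness and relatedness are already recorded for every AE. The stopping boundaries in 11.1 and 11.3 need no change for this purpose.
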